5. Women of childbearing potential with negative urine pregnancy test (UPT) at all visits (if UPT is positive, a blood test for human chorionic gonadotropin (hCG) to be performed) and who agree to follow highly effective birth control recommendations during the study and until 1 month after the end of the treatment. Birth control methods considered highly effective are: combined (estrogen and progestogen containing) hormonal contraception associated with inhibition of ovulation, progestogen-only hormonal contraception associated with inhibition of ovulation, intrauterine device (IUD), intrauterine hormone-releasing system (IUS), bilateral tubal occlusion, vasectomized partner or sexual abstinence. In each case of delayed menstrual period (over one month between menstruations, confirmation of absence of pregnancy is strongly recommended. This recommendation also applies to women of childbearing potential with infrequent or irregular menstrual cycles. A post-study contraception duration of 4 weeks is recommended taking into account the median half-life of Tadekinig alfa of almost 40h and 5 half-lives representing a duration of 200 hours.

EXCLUSION CRITERIA

1. Patients with life-threatening co-morbidities not associated with the underlying NLRC4-mutation or XIAP deficiency
2. Positive test for or prior history of HIV, Hepatitis B or Hepatitis C (serology)
3. Presence of active infections or a history of pulmonary TB infection with or without documented adequate therapy (QuantiFERON-TB test)
4. Presence of life-threatening infections (clinically and quantitated PCR if necessary)
5. Oncologic causes of symptoms; current or previous history of malignancy
6. Presence of CNS manifestations (i.e. seizures, altered mental status, signs of increased intracranial pressure, chronic papilledema, loss of vision, other sensorineural deficiencies, etc.)
7. Patients suffering from biallelic mutations in any of the following genes: PRF1/Perforin, UNC13D/Munc 13-4, STX11/Syntaxin11, STXB2/Munc 18-2, RAB27A/Rab27a (Griscelli syndrome type 2), LYST (Chediak-Higashi syndrome), AP3B1, ADTB3A, HPS2 mutations (Hermansky-Pudlak syndrome 2) and X-linked lymphoproliferative syndrome (XLP)-1 with SH2D1A mutation
8. Patients who are pregnant or nursing, women of childbearing potential who are unwilling to use highly effective birth control methods (see definition in Inclusion Criteria above) through 4 weeks after the end of their participation in the study

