- h W18/Visit 8 will serve as the End of the SAOL period visit for those patients who discontinued treatment during the SAOL phase (an early termination form should be completed for these patients). These patients will not continue into the RW phase of the study.
- i Treatment of study drug administered to patients at W18/Visit 8 would be determined by randomization into RW phase. Final dose of treatment under the SAOL phase of the study will occur 2 days prior to W18/Visit 8. All W18 assessments must be performed prior to administration of study drug at W18/Visit 8.
- K Height collected at screening
- l Collection of Baseline lab samples may occur up to 3 days prior to the scheduled Week 0/Day 0 and Week 18/ Day 126 visit in order to have results available to confirm patient eligibility prior to study treatment.
- m Flow cytometry studies are necessary when a XIAP genetic abnormality has been found in the genetic testing. It is not required for patients with NLRC4 genetic mutations.

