11.2.3 Patient Compliance

In order to enhance subjects' compliance, local skin treatment will be proposed to the parents/patients to mitigate local inflammatory reactions.

After patient discharge from the hospital the parents/patient will complete a daily diary recording current health status including body temperature, skin rash, vomiting, diarrhea, changes in concomitant medication, and any other unusual, remarkable symptoms.

NOTE: Temporary Stop of Treatment

Temporary treatment interruptions will be allowed in case the patient shows fever or any sign of undergoing an infection process unrelated to the treated condition. For the injections done by the home care nurse (HCN) every 2 days, the HCN should contact the Investigator for advice on treatment continuation or stopping. In case of any doubt, the treatment may be discontinued temporarily.

In case of treatment stop of more than 3 weeks the effect of the investigational drug is lost and the case will be considered a dropout (discontinuation).

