6 INVESTIGATIONAL PLAN

6.1 Overall Study Design

This is a Phase 3 study to assess the safety and efficacy of TA in patients with monogenic, IL-18 driven auto-inflammation due to NLRC4-MAS mutation or XIAP deficiency. Because of the likelihood for pathogenic IL-18 in certain monogenic diseases, patients known to harbor deleterious mutations in NLRC4-MAS or XIAP and who have a history of ongoing inflammation will be enrolled if they have ferritin \geq 500 ng/mL or persistent C-reactive protein (CRP) elevation \geq 2 times the upper limit of normal (ULN) and the patients have a Modified Auto-Inflammatory Disease Activity Index (mAIDAI) \geq 4.

This study is designed with SAOL of TA treatment duration for 18 weeks followed by a 16-week RW phase for efficacy and safety evaluation, with no interruption between the two phases of treatment. All patients who complete the 18 weeks of treatment during the SAOL phase and showing a partial or complete response at Week 18 (V8) will be randomized to one of the two treatment arms in a 1:1 ratio to begin treatment in the RW phase. Patients will receive the study treatment (placebo or TA) for up to an additional 16 weeks. During the RW phase, patients who develop a partial or full disease reactivation before the 16-week treatment is completed will proceed to the End of Study visit and complete the RW phase. The screening period will occur before the SAOL phase and before the first dose of Investigational Medicinal Product (IMP).

The physicians and the patients (or legal representative) will have the option to discontinue treatment if they feel that pursuing the treatment is not appropriate. The physician can decide any time to start rescue immunosuppression and therefore discontinue the patient from the study. In this case, all key safety and efficacy outcomes will be followed up. Patients will continue to come to the scheduled visits for safety and efficacy assessments. The occurrence of adverse events of severity grades 3 or 4 may result in transient or permanent treatment discontinuation. If treatment interruption is more than 3 weeks, the patient will be permanently discontinued from the study.

An estimated maximum of 15 patients will be enrolled in this study at approximately 11 clinical sites in the United States, Canada, and Germany. A maximum of 15 patients enrolled will ensure the randomization of at least 10 patients in the RW phase.

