7.5 Safety Evaluation

Safety analysis for data collected during the RW phase will be based on the RW-FAS, to include all patients who receive at least one dose of double-blind study drug during the RW phase. Patients who do not complete the study, for whatever reason, will have all available data up until the time of termination included in the analysis. For safety analysis presented by study visit, the RW Baseline value will be defined as the last value reported prior to the first dose of study drug during the RW phase.

All safety summaries for data collected during the SAOL phase will be based on the SAOL-FAS, to include all patients who receive at least one dose of TA during the SAOL phase. For safety analysis presented by study visit, the SAOL Baseline value will be defined as the last value reported prior to the first dose of TA during the SAOL phase.

7.5.1 *Extent of Exposure*

Extent of exposure to study treatment during the RW phase will be summarized for the RW-FAS by treatment group and during the SAOL phase for the SAOL-FAS for all patients combined. The duration of exposure will be presented in days and calculated as the date of last dose of study drug minus the date of first dose of study drug, plus one. The date of last dose of study drug is the date reported on the End of Treatment form, for both the end of the SAOL phase and the end of treatment during the RW phase. Duration of exposure and total number of doses received will be summarized using descriptive statistics.

7.5.2 *Adverse Events*

Treatment-emergent adverse events (TEAEs) are defined as those adverse events (AEs) with onset after the first dose of study drug or existing events that worsened after the first dose during the study. Treatment-emergent AEs occurring during the RW phase will be summarized by treatment group; TEAEs occurring during the SAOL phase will be summarized for all patients combined.

Treatment-emergent AEs occurring during the SAOL phase will be restricted to those events with onset on or after the start of dosing during the SAOL phase and prior to the start of dosing during the RW phase or 28 days after the last dose of study drug during

the SAOL phase, whichever occurs first. Events reported with a partial onset date (eg, month and year are reported but the day is missing) will be considered to be treatment-emergent if it cannot be confirmed that the event onset was prior to the first dose of study drug based on the available date entries.

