Treatment-emergent AEs occurring during the RW phase will be restricted to those events with onset on or after the start of dosing during the RW phase and prior to the first dose of study drug during the open-label extension study or 28 days after the last dose of study drug during the RW phase, whichever occurs first.

Verbatim terms on case report forms will be mapped to preferred terms and system organ classes using the Medical Dictionary for Regulatory Activities (MedDRA, version 20.0).

Summaries that are displayed by system organ class and preferred terms will be ordered by descending incidence of system organ class and preferred term within each system organ class. Summaries displayed by preferred term only will be ordered by descending incidence of preferred term. Terms with the same incidence will be ordered alphabetically. Summaries of the following types will be presented, separately for the SAOL phase and RW phase:

- Overall summary of number of unique TEAEs and treatment-emergent serious adverse events (SAEs) and patient incidence of TEAEs meeting various criteria
- Patient incidence of TEAEs by MedDRA system organ class and preferred term
- Patient incidence of TEAEs by severity grade, MedDRA system organ class, and preferred term
- Patient incidence of TEAEs by relationship to study drug, MedDRA system organ class, and preferred term
- Patient incidence of TEAEs with severity grade ≥ 3 and related to study drug by MedDRA system organ class and preferred term
- Patient incidence of treatment-emergent adverse events of special interest (AESI) by MedDRA system organ class and preferred term
- Patient incidence of SAEs by MedDRA system organ class and preferred term

At each level of summarization (eg, any AE, system organ class, and preferred term), patients experiencing more than one TEAE will be counted only once. In the summary of TEAEs by severity grade, patients will be counted once at the highest severity reported at each level of summarization; in the summary of TEAEs by relationship, patients will be counted once at the closest relationship to study drug.

In addition to the TEAE incidence summaries described above, TEAE incidence will be corrected for differences in study drug exposure by using person-time in the denominator

to calculate incidence rates. Each patient's person exposure years (PEY) will be calculated by the following:

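### SAP 7.5.2 applies its 28-day post-dose tail inconsistently, so a delayed Tadekinig alfa event early in the RW phase would be tabulated under placebo with no carry-over split

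*SAP*

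**What the plan says.** SAP 7.5.2 defines two event windows.

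- **SAOL window.** It runs from the first SAOL dose until "prior to the start of dosing during the RW phase or 28 days after the last dose of study drug during" the SAOL phase, whichever is earlier.
- **RW window.** RW events "will be restricted to those events with onset on or after the start of dosing during the RW phase". The window ends at the first dose of the extension study or "28 days after the last dose of study drug during the RW phase, whichever occurs first".

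On presentation, the SAP states: "Treatment-emergent AEs occurring during the RW phase will be summarized by treatment group". Exposure-adjusted rates are given separately for each phase. A patient without the event of interest contributes person-time from first dose to last dose plus 28 days.

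Four other statements matter here:

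- The phases run "with no interruption between the two phases of treatment" (SAP 6.1).
- "Final dose of treatment under the SAOL phase of the study will occur 2 days prior to W18/Visit 8" (Protocol Section 7, Table 1 footnote i).
- The contraception criterion cites a "median half-life of Tadekinig alfa of almost 40h and 5 half-lives representing a duration of 200 hours" (Protocol Synopsis, inclusion criterion 5).
- "In case of treatment stop of more than 3 weeks the effect of the investigational drug is lost" (Protocol 11.2.3).

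SAP 7.5.2 contains no carry-over flag, lagged window or sensitivity table for early RW. It does plan tables by relationship to study drug and by-patient listings of all adverse events.

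**The concern.** Every patient randomised to placebo has just had 18 weeks of Tadekinig alfa and took the last dose 2 days before RW Day 1. Take an event 20 days after the last open-label dose. If the patient stopped in the SAOL phase, it is counted as a Tadekinig alfa event. If the patient was randomised to placebo, it goes in the placebo column. If the patient was randomised to Tadekinig alfa, it stays with the drug. A delayed drug effect can therefore only move towards placebo, which would make the arms look more alike.

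The RW phase is the only concurrent controlled safety comparison in the current design. With 5 placebo patients planned, one relocated event changes an arm's incidence by 1/5 = 20 percentage points. Placebo patients are also expected to reactivate and leave early, so the first weeks make up much of all placebo follow-up.

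**Working it through.** **1. The stated clock.** 5 × 40 h = 200 h = 8.3 days, which reproduces the protocol's figure. By first-order decay, the level left at the first placebo dose (48 h) is 0.5^(48/40) = 44%. At 28 days (672 h) it is 0.5^(672/40), under 0.001%.

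**2. How far each clock reaches into RW.** Subtract the 2-day gap before RW Day 1.

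| Window after last open-label dose | Days into RW | Share of 16 weeks (112 d) | Share of 8 weeks (56 d) |
|---|---|---|---|
| 28 days (SAP tail) | 26 | 23% | 46% |
| 21 days (protocol's 3-week statement) | 19 | 17% | 34% |
| 200 h | 6.3 | 5.7% | 11% |

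The 8-week column applies to patients under protocol versions 4.0/4.1 and earlier. On the SAP's inclusive day count, 26 elapsed days is RW Day 27, so Days 1 to 27 lie within 28 days of the last open-label dose.

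**3. Share of placebo follow-up at the plan's 90% event rate (SAP 7.6).** Assume exponential reactivation times with follow-up ending at reactivation or Day 112. The hazard is λ = −ln(0.1)/112 = 0.02056 per day, and S(t) = exp(−λt).

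*Reactivation detected at once:*
- Mean follow-up = (1 − 0.1)/λ = 43.8 days (6.3 weeks).
- Time in the first 26 days = (1 − S(26))/λ = (1 − 0.586)/0.02056 = 20.1 days. Share 20.1/43.8 = 46%.
- Time in the first 6.3 days = (1 − 0.8785)/0.02056 = 5.91 days. Share 5.91/43.8 = 13.5%.

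*Reactivation detected only at RW weeks 2, 4, 8, 12 and 16:*
- Mean follow-up = 14 + 14(0.750) + 28(0.562) + 28(0.316) + 28(0.178) = 54.1 days (7.7 weeks).
- Time in the first 26 days = 14 + 12(0.750) = 23.0 days. Share 23.0/54.1 = 42.5%.
- First 6.3 days: 6.3/54.1 = 11.6%.

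*Adding the full 28-day tail after the last RW dose:*
- 28-day window: 26/(43.8 + 28) = 36% and 26/(54.1 + 28) = 32%.
- 200 h: 6.3/71.8 = 8.8% and 6.3/82.1 = 7.7%.

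The same calculation at assumed placebo event rates of 50–70% gives 29–35% for the 28-day window without the tail.

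**4. SAOL person-time.** Use nominal days: first SAOL dose Day 0, last SAOL dose Day 124, first RW dose Day 126. Read the formula with phase-specific dose dates.
- Credited to an event-free patient: 124 − 0 + 1 + 28 = 153 days.
- Days over which a SAOL event can count (Days 0 to 125): 126.
- The denominator is 153/126 − 1 = 21% too long. A rare-event rate is multiplied by 126/153 = 0.82.

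The surplus 153 − 126 = 27 days is RW Days 1 to 27. Events on those days are counted in RW, under placebo for placebo patients.

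**The case against.** A reader might infer that the SAP breaks its own rule because these patients are still inside the Tadekinig alfa window. They are not: the SAOL window ends at the earlier of two dates, and for anyone entering RW on schedule that is the first RW dose. Nor does the rule differ by arm. Both arms had the same 18 weeks of drug and both are tabulated by randomised group from RW Day 1. That is the comparison the design offers: continuing against withdrawing.

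A reader might also infer that early placebo events vanish as drug events. They do not. The SAP tabulates RW events by relationship to study drug, and Protocol 17.7.2 requires a possibly related call unless causality can be excluded. By-patient listings remain, and with about 5 placebo patients each event can be read individually. What these tables cannot do reliably is separate residual drug from placebo, because RW causality is judged blind and the tables are split by phase.

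Two further points stand. On a 40 h half-life, 28 days is 16.8 half-lives, so the largest figures come from the longest window. And a later-period comparison is no longer randomised. By RW Day 27, 25–41% of placebo patients would already have left under the plan's assumptions, against 3–5% on Tadekinig alfa at a hazard ratio of 0.1.

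**Conclusion.** The inconsistency is real. The 28-day tail operates after SAOL discontinuation, after the last RW dose and in person-time, but not for events in patients who cross from SAOL to RW. The consequence is a possible bias in one direction, towards a smaller difference between the arms. The documents give no evidence that delayed Tadekinig alfa harms occur.

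Placebo time open to carry-over at the 90% event rate is 42.5–46% on the 28-day clock (32–36% with the post-RW tail) and about 12–13.5% on the 200 h clock (8–9% with the tail). It is tempting to read these as the proportion of placebo events carrying the wrong label. They are not: under a constant background rate most events in those days would have occurred anyway, and only an excess caused by residual drug would be misplaced. The documents give no basis for estimating that excess.

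The person-time mismatch does not depend on delayed harms. It makes a rare-event SAOL rate about 18% too low for patients who enter RW, if the formula is read with phase-specific dates.

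The shares rest on exponential reactivation times, no other dropout and a 16-week RW phase. Safety is descriptive, so interpretation is affected; the primary efficacy test is not.

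**What to change.** In SAP 7.5.2, before unblinding:

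1. Keep the current by-arm RW table as the main one.
2. Add a descriptive table, in both arms, that splits RW events and person-time by time since the last open-label dose: within 28 days (RW Days 1 to 27 when that dose was 2 days before RW Day 1) and later (RW Day 28 onward). Use the 200 h cut as an alternative.
3. State beside it that the later interval holds few, selected placebo patients (59–75% still in RW at the plan's 90% event rate) and is not a randomised comparison.
4. End SAOL person-time at the first RW dose for patients who enter RW.

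The cost is one extra table with small numbers and one changed line in the person-time definition. No new data are needed.

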17 HANDLING OF ADVERSE EVENTS

17.1 Non-Serious and Serious Adverse Events

An adverse event (AE) is any undesirable sign, symptom, or medical condition occurring after signing the Informed consent form (ICF) through the end of study at follow up (V13).

Information about all AEs, whether volunteered by the subject, discovered by questioning, or detected through physical examination, laboratory testing, or other means, will be collected and recorded on the AE CRF page and followed as appropriate.

All relevant medical conditions present prior to study entry will be documented in the Medical History CRF. However, medical conditions occurring after signing the ICF are to be recorded as AEs. This includes worsening of a pre-existing condition. AEs occurring prior to administration of study drug will be considered non-treatment emergent, and those occurring after the start of study drug will be considered treatment emergent.

Adverse events will be monitored and recorded from the time the informed consent is signed. The Investigator is responsible for the detection and documentation of events meeting the criteria and definition of an AE, an SAE and an AE of special interest (AESI) as provided in this protocol (see [Sections 17.2](#) and [17.3](#)). All AEs (including AESIs) and SAEs will be recorded in the source documents. AEs will be entered on the appropriate eCRF page from the time of signing informed consent until completion of the study (Visit 13) or premature withdrawal.

Throughout the study, during clinic visits, home visits and other contacts, after the patient has had an opportunity to spontaneously mention any problems, the Investigator should inquire about the occurrence of AEs. The HCN will inquire about potential AEs at the moment of treatment administration. If an AE is reported, the nurse will communicate to the site responsible physician. The following are examples of open-ended questions that may be used to obtain this information at the sites during the programmed visits or by the home care nurse:

- "How are you feeling?"
- "Have you had any medical problems since your last visit/assessment?"
- "Have you taken any new medicines, other than those given to you in this study, since your last visit/assessment?"

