17.7.6 Post-study Adverse Events or Serious Adverse Events

Investigators are not obligated to actively seek AEs or SAEs in former study participants. However, the Investigator should promptly notify the Sponsor, or designee, if the Investigator learns of any SAE or death of a study patient within 30 days after a patient has been discontinued from the study, and such event(s) is (are) reasonably related to study participation; these should be reported within 24 hours.

Investigators should promptly notify the Sponsor, or designee, if they become aware of a former study participant who is one of the parents of a subsequently conceived child with a congenital anomaly (see Section 17.4 on Pregnancy Information).

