- As the date of onset of the TEAE of interest minus the date of first dose of study drug plus one, divided by 365.25, for those subjects who experience the TEAE of interest; or
- As the date of last dose of study drug plus 28 days, minus the date of first dose of study drug plus one, divided by 365.25, for those subjects who do not experience the TEAE of interest.

One PEY is the equivalent of one patient exposed to study drug for one year. Two patients who are exposed to study drug for half a year contribute one PEY. The total PEY of a treatment group is the sum of the person exposure years of each patient in that treatment group. Exposure-adjusted TEAE incidence will be summarized per 100 PEY as the number of patients with an event for whom person-time is available, divided by the total PEY for each treatment group and multiplied by 100. Exposure-adjusted TEAE incidence will be summarized separately for the SAOL phase and the RW phase.

Adverse event data will be presented in data listings by patient, treatment group, and event. Serious AEs, AEs leading to discontinuation of the study drug, and AESIs will be presented in separate data listings.

7.5.3 *Deaths, Other Serious Adverse Events, and Other Significant Adverse Events*

All deaths during the study as reported on the End of Treatment (SAOL), End of Treatment (RW), Study Completion/Study Discontinuation, and Adverse Event eCRFs will be listed by patient, to include the primary cause of death. Serious AEs, AEs leading to study drug withdrawal, interruption, or dose reduction of the study drug, and AESIs will be provided in separate patient data listings. AESIs include events that constitute an injection site reaction, including pruritus, erythema, and swelling.

7.5.4 *Clinical Laboratory Evaluation*

All descriptive summaries of laboratory results will be based on data analyzed by the central laboratory and presented in Système International (SI) units, as suggested by the Center for Biologics Evaluation and Research and the Center for Drug Evaluation and Research *Position on Use of SI Units for Lab Tests* (Oct 2013). All data will be included in by-patient data listings. Laboratory measurements identified as abnormal (ie, outside the normal range) will also be listed separately by patient, laboratory test, and unit. In addition, normal ranges provided by the central laboratory will be presented in a separate listing.

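### SAP 7.5.2 runs event-free person-time to 28 days after the last dose without the cap that closes the adverse event window, so some exposure-adjusted rates are too low

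*SAP*

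**What the plan says.** SAP 7.5.2 gives the purpose of the extra table: "TEAE incidence will be corrected for differences in study drug exposure by using person-time in the denominator". A patient with the event contributes time up to its onset. A patient without it contributes time calculated as "As the date of last dose of study drug plus 28 days, minus the date of first dose of study drug plus one"; the result is then converted from days to years. The section explains the unit by example: "Two patients who are exposed to study drug for half a year contribute one PEY". Rates are reported separately for SAOL and RW.

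The same section limits which events count. An SAOL event must start "prior to the start of dosing during the RW phase or 28 days after the last dose of study drug", and an RW event "prior to the first dose of study drug during the open-label extension study or 28 days after the last dose of study drug"; in both cases the earlier limit applies.

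Three protocol provisions fix the timing:

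- Table 1, footnote i: "Final dose of treatment under the SAOL phase of the study will occur 2 days prior to W18/Visit 8". The first RW dose is given at that visit, Day 126.
- Section 17.1: adverse events are entered "from the time of signing informed consent until completion of the study (Visit 13) or premature withdrawal".
- Section 17.7.6: afterwards investigators need not actively seek events. An investigator who "learns of any SAE or death of a study patient within 30 days after a patient has been discontinued from the study" notifies the sponsor if the event is reasonably related to participation.

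**The concern.** A rate is interpretable when the denominator covers the time during which an event could enter the numerator. Here the numerator window has an earlier-of rule and the denominator does not. Where the next phase starts soon after the last dose, most of the added 28 days cannot yield an event for the phase being reported, so the rate per 100 person-years is too low.

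The added time is also fixed, so it weighs more on short exposure. If one RW arm leaves sooner than the other, a table intended to remove the effect of unequal exposure retains part of it. At stake is the accuracy of a descriptive safety table. No hypothesis test or stopping rule uses these rates.

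**Working it through.** The documents state no person-time total or exposure-adjusted rate, so there is no planned figure to reproduce. The check is a day count.

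**Inputs**

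- Visit 1 = Day 0, Visit 8 = Day 126, Visit 13 = Day 238 (Protocol 14.3, 14.7, 14.9). Visit 13 is therefore 112 days after the first RW dose.
- Last SAOL dose = Day 124; first RW dose = Day 126 (Protocol Table 1, footnote i).
- First and last dose are read as phase-specific, because the rates are reported by phase.
- With d = last dose day − first dose day, event-free person-time is d + 28 + 1 = d + 29 days.
- Shortfall = 1 − (days in which an event could be counted) / (SAP person-days). This is the limit for an uncommon event, where almost every patient is event-free.

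**SAOL patient moving into RW**

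- Person-days: 124 + 29 = 153 (Days 0 to 152).
- Event window: Days 0 to 125 = 126 days.
- Shortfall: 27/153 = 17.6%. The denominator is 27/126 = 21% above the window.
- Days 126 to 152, the 27 extra days, are also in the RW denominator.

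**Whole SAOL phase**

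A patient who stops in SAOL has a window that does run to last dose + 28 days, so there is essentially no mismatch. SAP 6.1 plans at most 15 enrolled and at least 10 randomized. Assume 10 move on and 5 stop after 14 to 125 exposure days:

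- 14 days: person-days 10 × 153 + 5 × 42 = 1740; window 10 × 126 + 5 × 42 = 1470; shortfall 270/1740 = 15.5%.
- 125 days: person-days 10 × 153 + 5 × 153 = 2295; window 10 × 126 + 5 × 153 = 2025; shortfall 270/2295 = 11.8%.

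**Common events**

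A patient with the event gets no added 28 days. For patients moving into RW, with a constant hazard over 126 days, reported/true is 0.871 if half have the event (13% low) and 0.921 if 80% do (8% low).

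**16-week RW completer**

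| Case | Person-days | Countable days | Shortfall |
|---|---|---|---|
| Extension starts 2 days after last dose (assumed); d = 110 | 139 | 112 | 27/139 = 19.4% |
| Same; d = 112 | 141 | 114 | 27/141 = 19.1% |
| No extension, against the event window; d = 110 | 139 | 138 | 1/139 = 0.7% |
| No extension, entry ends at Visit 13; d = 110 | 139 | 113 | 26/139 = 18.7% |
| No extension, entry ends at Visit 13; d = 112 | 141 | 113 | 28/141 = 19.9% |
| No extension, final visit 2 days after last dose; d = 112 | 141 | 115 | 26/141 = 18.4% |

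**Between arms (illustration only)**

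Assume a true Tadekinig alfa:placebo rate ratio of 1.0, exponential time to reactivation, exit on reactivation, and adverse event collection ending at exit. Use the planning rates in SAP 7.6 (90% on placebo, hazard ratio 0.1).

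- Exit at the next scheduled visit: mean exit day 102.5 against 54.1. Observed shares are (102.5 + 1)/(102.5 + 29) = 0.787 and (54.1 + 1)/(54.1 + 29) = 0.663. Apparent ratio 0.787/0.663 = 1.19.
- Exit at the event itself: 0.783/0.618 = 1.27.
- If the final visit falls 2 days after the last dose: 0.799/0.679 = 1.18 and 0.795/0.635 = 1.25.
- With 70% placebo reactivation the ratio is 1.08-1.13; with 50% it is 1.04-1.07.

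**The case against.** The 28 days are not arbitrary. The SAP counts events for up to 28 days after the last dose, so including post-dose time in the denominator is coherent. The half-year example can be read as explaining the unit, with the formula as the operative definition. This stands: literal disagreement with the example (two event-free patients would contribute 2 × (182.625 + 28)/365.25 = 1.15 person-years) is not the main defect.

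For two groups the rule agrees with the window: patients who stop during SAOL, and RW patients who do not enter the extension. Protocol 9.1 also keeps patients who stop treatment under follow-up, so some added days are observed. This stands too. For RW patients outside the extension, the shortfall rests only on routine entry ending at Visit 13 or withdrawal, and related serious events and deaths can still be notified under Protocol 17.7.6.

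The between-arm ratios are modelled. The largest use the 90% placebo rate, although Protocol 16.3 reports that fewer events than first expected were seen. SAP 6.1.5 limits the rule that reactivators leave the study to protocol versions 5.0 and later. If placebo patients leave sooner, the distortion makes Tadekinig alfa look relatively worse, so it does not favor the drug.

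None of this answers the mismatch for patients moving from SAOL into RW, which follows from the dosing schedule and the SAP's own window.

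**Conclusion.** The person-time rule is wrong as written for patients who go straight into a next phase. The firm result is 153 days against 126: about 18% understatement of an uncommon TEAE for each SAOL patient moving into RW, with 27 days counted twice. The 12-16% phase-level figure rests on the assumed 10-of-15 split and stopping times. The 19% in RW rests on assumed extension timing, which the documents do not give.

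Three stronger readings might be inferred, and the documents do not support them:

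- That the whole SAOL table is 18% low. It is not, because the window for SAOL discontinuers already runs to last dose + 28 days.
- That RW person-time overruns the event window for everyone. It does so only for patients who start the extension within 28 days of their last dose. For the others the 18-20% is a limit of adverse event collection, with exceptions for related serious events and deaths.
- That the treatment comparison is biased by a known amount. Some distortion is possible if placebo patients leave sooner, but the 1.04-1.27 range depends on assumed exit and collection timing.

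The consequence is confined to descriptive tables with about 5 patients per RW arm. Plain incidence is unaffected, and SAOL is single-arm, so no between-arm question arises there. The rule should still be corrected, because readers will take rates per 100 person-years at face value.

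**What to change.** In SAP 7.5.2, end event-free person-time at the earlier of the first dose of the next phase (RW or extension) and last dose + 28 days, matching the TEAE windows. For patients who do not enter a next phase, end it no later than the last visit or contact at which adverse events were assessed. Adjust the half-year example to agree with the formula.

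Leave the TEAE windows and the plain incidence tables unchanged. In the exposure-adjusted table, footnote any later event notified under Protocol 17.7.6 so that no related serious event or death drops out of view.

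With this change an SAOL patient moving into RW contributes 126 days instead of 153, and a 16-week RW completer about 112-113 days instead of 139-141 if the extension starts at Visit 13 or entry ends there. The cost is slightly more programming and somewhat higher reported rates. No new data and no protocol amendment are needed.
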